##### **5.3.2.1. Reasons for Permanent Discontinuation of Study Drug**

Study drug dosing will be permanently stopped in the event of:

- A patient being randomized under amendment 3 or a subsequent amendment and treated with the 3 mg Q4W or 6 mg Q8W dosing regimen
- A patient being randomized under an earlier version of the protocol before amendment 3 and treated with the 6 mg Q4W, 9 mg Q4W, or placebo Q4W dosing regimen
- A subject developing clinically significant sensory and motor neurologic events confirmed by a neurologist's examination and graded by the neurologist as at least

moderate peripheral neuropathy limiting activities of daily living, ie, grade  $\geq 2$  according to v.4 (CTCAE); study sites should use CTCAE v.4 criteria throughout the study for consistency

- Evidence of pregnancy
- A patient developing new or worsening signs and symptoms indicative of carpal tunnel syndrome
- Continued noncompliance with protocol-defined maximum NSAID use (see Section 4.3) after appropriate counseling
- Continued noncompliance with protocol-defined maximum acetaminophen/paracetamol use (with a maximum daily dose of 2500 mg in Europe and other countries where 500 mg strength tablets/capsules are available and 2600 mg in any countries outside of Europe where 325 mg strength tablets/capsules are available) after appropriate counseling
- JR Surgery
- AESI:
  - Adjudicated arthropathy, as described in Section 7.6.1.1
  - Sympathetic nervous system dysfunction, as described in Section 7.6.1.2
- Hepatotoxicity
  - Study drug should be discontinued if:
    - a) Total bilirubin (TBL)  $>2x$  ULN or international normalized ratio (INR)  $>1.5$  and
    - b) Alanine aminotransferase (ALT) or aspartate aminotransferase (AST)  $>3x$  ULN and
    - c) No other cause for a and b is readily apparent

Other causes of ALT, AST, and TBL elevations can include alcoholic hepatitis, autoimmune hepatitis, non-alcoholic hepatitis, heritable diseases (Gilbert's Syndrome), heart failure, and viral hepatitis.

Study drug may be withheld in patients who do not meet criteria for permanently discontinuing study drug, until an alternative cause for drug-induced liver injury can be determined. The patient may be re-challenged if an alternative cause for elevated liver function tests is found and the liver function tests return to baseline, but only after discussion with the sponsor.

- Systemic hypersensitivity reaction assessed as related to study medication

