Adverse events	X	X
Vital signs	X	X
Orthostatic blood pressure ⁴	X	X
Physical examination with joint exam	X ¹	X
Medical history related to the joint replacement	X	X
Joint pain questionnaire	X	X
Post-operative assessment questionnaire ²	X	X
Bilateral radiograph (knee, hip, shoulder) ⁵	X ⁶	X
Event-triggered imaging ³	X	X

F/U: Follow-up

- All available information for patients who undergo JR surgery must be collected, including placement of the prosthesis, healing of the surgical wound, and the results of the histopathologic examination.
- Knee Society Score questionnaire for knee replacements or Harris Hip Score questionnaire for hip replacements.
- Imaging (x-ray and/or MRI) will be performed on any joint following a report of clinically significant worsening or exacerbation of pain in that joint.
- If it is not possible to obtain orthostatic blood pressure following JR then blood pressure and pulse should be recorded.
- In the event of more than 1 JR, imaging assessments should be repeated if it has been >60 days since the joints were last imaged. If it has been ≤60 days since imaging assessments were completed, imaging assessments may be completed at the discretion of the investigator. An MRI may be requested by the imaging vendor after review of the x-rays.
- Imaging will be done at week 4 if not done pre-operatively.

11.2. Reference for Criteria for Treatment-Emergent Potentially Clinically Significant Values (PCSV)

The PCSV criteria below should be used as a reference; the actual criteria for each study should be determined and agreed to by the study team prior to database lock as part of SAP and should be based on the study population, indication, and potential effects of study treatment.

Table 2: Criteria for Treatment-Emergent Potentially Clinically Significant Values (PCSV)

Parameter	Treatment Emergent PCSV	Comments
Clinical Chemistry		
ALT*	>3 and ≤ 5 ULN and baseline ≤ 3 ULN*	Enzyme activity must be expressed in ULN, not in IU/L.
	>5 and ≤ 10 ULN and baseline ≤ 5 ULN	FDA DILI Guidance July 2009.
	>10 and ≤ 20 ULN and baseline ≤ 10 ULN	Each category is calculated independently.
	>20 ULN and baseline ≤ 20 ULN	* At least one level is required; multiple levels are optional for phase 2/3 studies. If it is desirable to get the distribution across the different PCSV levels, additional shift table on ≤3, >3 to ≤5, >5 to ≤10, >10 to ≤20, and >20 category for baseline vs. post baseline may be provided

Parameter	Treatment Emergent PCSV	Comments

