AST*	
>3 and ≤ 5 ULN and baseline ≤ 3 ULN*
 
>5 and ≤ 10 ULN and baseline ≤ 5 ULN
 
>10 and ≤ 20 ULN and baseline ≤ 10 ULN
 
>20 ULN and baseline ≤ 20 ULN
	
Enzyme activity must be expressed in ULN, not in IU/L.
 
FDA DILI Guidance July 2009.
 
Each category is calculated independently.
 
* At least one level is required; multiple levels are optional for phase 2/3 studies. If it is desirable to get the distribution across the different PCSV levels, additional shift table on ≤3, >3 to ≤5, > 5 to ≤10, >10 to ≤20, and >20 category for baseline vs. post baseline may be provided

Alkaline Phosphatase	>1.5 ULN and baseline ≤ 1.5 ULN	
Enzyme activity must be expressed in ULN, not in IU/L.
 
FDA DILI Guidance July 2009.

Total Bilirubin*	
>1.5 and ≤ 2 ULN and baseline ≤ 1.5 ULN*
 
>2 ULN and baseline ≤ 2.0 ULN
	
Must be expressed in ULN, not in μmol/L or mg/L. Categories are cumulative.
 
FDA DILI Guidance July 2009.
 
* At least one level is required; multiple levels are optional for phase 2/3 studies. If it is desirable to get the distribution of significant level, additional shift table on ≤1.5, >1.5 to ≤2.0 and > 2.0 category for baseline vs. post baseline may be provided

Conjugated Bilirubin	(Direct Bilirubin >35% Total Bilirubin and Total Bilirubin >1.5 ULN) and (Direct Bilirubin ≤35% Total Bilirubin or Total Bilirubin ≤1.5 ULN) at baseline	Conjugated bilirubin dosed on a case-by-case basis.

Parameter	Treatment Emergent PCSV	Comments
ALT/AST and Total Bilirubin	
(ALT >3 ULN and TBILI>2 ULN) and baseline (ALT <=3 ULN or TBILI <=2 ULN)
 
(AST >3 ULN and TBILI>2 ULN) and baseline (AST <=3 ULN or TBILI <=2 ULN)
 
(ALT >3 ULN and TBILI>1.5 ULN) and baseline (ALT <=3 ULN or TBILI <=1.5 ULN)
 
(AST >3 ULN and TBILI>1.5 ULN) and baseline (AST <=3 ULN or TBILI <=1.5 ULN)
	FDA DILI Guidance July 2009.
ALT/AST and Total Bilirubin and ALP	
(ALT >3 ULN and TBILI>2 ULN and ALP < 2 ULN) and baseline (ALT <=3 ULN or TBILI <=2 ULN or ALP >=2 ULN)
 
(AST>3 ULN and TBILI>2 ULN and ALP < 2 ULN) and baseline (AST <=3 ULN or TBILI <=2 ULN or ALP >=2 ULN)
	FDA DILI Guidance July 2009.

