CPK*	
>3 and ≤ 10 ULN and baseline ≤ 3ULN*
 
>10 ULN and baseline ≤ 10ULN
	
FDA Feb 2005.
 
Am J Cardiol April 2006.
 
Categories are cumulative.
 
* At least one level is required; multiple levels are optional for phase 2/3 studies. If it is desirable to get the distribution of significant level, additional shift table on ≤3, >3 to ≤10, and > 10 category for baseline vs. post baseline may be provided

Parameter	Treatment Emergent PCSV	Comments
Creatinine	$\geq 150 \mu\text{mol/L}$ (Adults) and baseline $< 150 \mu\text{mol/L}$ $\geq 30\%$ change from baseline and $< 100\%$ change from baseline $\geq 100\%$ change from baseline	Benichou C., 1994 3 independent criteria
Uric Acid		Harrison - Principles of internal Medicine 17 th Ed., 2008.
Hyperuricemia	$> 408 \mu\text{mol/L}$ and $\leq 408 \mu\text{mol/L}$ at baseline	Two independent criteria
Hypouricemia	$< 120 \mu\text{mol/L}$ and $\geq 120 \mu\text{mol/L}$ at baseline	
Blood Urea Nitrogen	$\geq 17 \text{ mmol/L}$ and $< 17 \text{ mmol/L}$ at baseline	Two independent criteria
Chloride		Two independent criteria
Hypochloremia	$< 80 \text{ mmol/L}$ and baseline $\geq 80 \text{ mmol/L}$	
Hyperchloremia	$> 115 \text{ mmol/L}$ and baseline $\leq 115 \text{ mmol/L}$	
Sodium		Two independent criteria
Hyponatremia	$\leq 129 \text{ mmol/L}$ and baseline $> 129 \text{ mmol/L}$	
Hypernatremia	$\geq 160 \text{ mmol/L}$ and baseline $< 160 \text{ mmol/L}$	
Potassium		FDA Feb 2005.
Hypokalemia	$< 3 \text{ mmol/L}$ and baseline $\geq 3 \text{ mmol/L}$	Two independent criteria
Hyperkalemia	$\geq 5.5 \text{ mmol/L}$ and baseline $< 5.5 \text{ mmol/L}$	
Total Cholesterol	$\geq 7.74 \text{ mmol/L}$ and $< 7.74 \text{ mmol/L}$ at baseline	Threshold for therapeutic intervention.

[figure not shown]
Parameter	Treatment Emergent PCSV	Comments
Triglycerides	≥4.6 mmol/L and < 4.6 mmol/L at baseline	Threshold for therapeutic intervention.
Glucose		
Hypoglycaemia	(≤3.9 mmol/L and <LLN) and (>3.9 mmol/L or ≥LLN) at baseline	ADA May 2005.
Hyperglycaemia	≥11.1 mmol/L (unfasted); ≥7 mmol/L (fasted) and < 11.1 mmol/L (unfasted); <7 mmol/L (fasted) at baseline	ADA Jan 2008.
HbA1c	>8% and ≤ 8% at baseline	
Albumin	≤25 g/L and >25 g/L at baseline	
hs-CRP	2 ULN or > 10 mg/L (if ULN not provided)	FDA Sept. 2005
Hematology		

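### PCSV levels below the top one for ALT, AST, total bilirubin and CPK have upper caps, so a table with the stated minimum of one level can omit the highest values, and no row counts everyone above the lowest threshold

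*SAP*

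**What the plan says.** SAP 11.2 Table 2 sets these treatment-emergent levels, each with a baseline condition at its own lower bound:

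- **ALT and AST:** ">3 and ≤ 5 ULN and baseline ≤ 3 ULN", then ">5 and ≤ 10 ULN and baseline ≤ 5 ULN", then ">10 and ≤ 20 ULN and baseline ≤ 10 ULN", then an open level above 20 ULN. The comment says the categories are calculated independently.
- **Total bilirubin:** ">1.5 and ≤ 2 ULN and baseline ≤ 1.5 ULN", then an open level above 2 ULN. The comment says "Categories are cumulative".
- **CPK:** ">3 and ≤ 10 ULN and baseline ≤ 3ULN", then an open level above 10 ULN. It carries the same cumulative comment.

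For all four tests an asterisk on the parameter name and on the first level leads to the note "At least one level is required; multiple levels are optional for phase 2/3 studies". A shift table across all bands is offered only as an option.

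The appendix introduces its criteria as a reference, to be settled by the study team before database lock as part of the SAP. SAP 4.5.4, 5.1.7 and 5.1.8.3 all point to this appendix for the definition, and no other definition is given for these tests. SAP 5.1.7 uses all on-treatment post-baseline values, scheduled and unscheduled. SAP 5.1.8.3 commits to summarising PCSVs by treatment group.

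**The concern.** A threshold row should rise, or at least not fall, as patients get worse. A capped row does not behave that way: moving a patient from 4 to 8×ULN takes that patient out of the first ALT row. If the first row is the only one produced, which the note permits, the between-arm comparison can be flat while severe elevations differ.

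With every level reported, the reader still cannot read off the number of patients above 3×ULN. Adding the rows may double-count, because one patient can have values in several bands and the SAP does not say that only the worst value counts.

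The cumulative label on bilirubin and CPK tells a programmer to count a bilirubin of 3×ULN in the lower row, while the printed criterion excludes it. Two programmers could produce different tables from the same text.

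Change in safety laboratory results is part of the primary endpoint (Protocol 8.2; SAP 4.5.1), so these tables should be unambiguous.

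**Working it through.** The plan states no figure to reproduce here. The check applies the criteria as printed.

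**1. Are the levels disjoint?** For each test, compare the cap of one level with the lower bound of the next. ALT/AST: 5 = 5, 10 = 10, 20 = 20. Bilirubin: 2 = 2. CPK: 10 = 10. All levels are disjoint and all top levels are open. The cumulative comment is therefore wrong for bilirubin and CPK. The comment on ALT and AST does not contradict disjoint bands.

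**2. Who is counted?** Illustrative patients, baseline 1×ULN (assumed):

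| Post-baseline value(s), ×ULN | First level as printed | Other printed level met | First level if open-ended |
|---|---|---|---|
| ALT 4 | yes | none | yes |
| ALT 6 | no | >5 to ≤10 | yes |
| ALT 12 | no | >10 to ≤20 | yes |
| ALT 25 | no | >20 | yes |
| ALT 4, then 12 | yes if any value counts; no if only the worst counts | >10 to ≤20 | yes |
| Bilirubin 3 | no | >2 | yes |
| CPK 12 | no | >10 | yes |

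**3. Effect on a between-arm comparison (assumed counts).** Take 1,000 patients per arm. In each arm 10 have ALT only in >3 to ≤5 ULN. A further 12 v 2 have ALT only above 5 ULN.

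- Capped first row: 10 v 10, ratio 10/10 = 1.0.
- Open >3 ULN row: (10 + 12) v (10 + 2) = 22 v 12, ratio 22/12 = 1.83.

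**4. Direction of the effect (assumed distribution).** Suppose peak ALT among patients who react is lognormal with median m and log-SD s, and the peak is the value counted. Then

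- share in the band = Φ(ln(5/m)/s) − Φ(ln(3/m)/s)
- share above 3 ULN = 1 − Φ(ln(3/m)/s)

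With s = 0.6:

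- m = 4: Φ(0.372) − Φ(−0.479) = 0.645 − 0.316 = 0.33; above 3 ULN, 0.68.
- m = 8: Φ(−0.783) − Φ(−1.635) = 0.217 − 0.051 = 0.17; above 3 ULN, 0.95.

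So doubling the median peak halves the band share while the share above 3 ULN rises. The same formulas over a range of s:

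| s | Band share, m = 4 → 8 | Above 3 ULN, m = 4 → 8 |
|---|---|---|
| 0.4 | 0.48 → 0.11 | 0.76 → 0.99 |
| 0.6 | 0.33 → 0.17 | 0.68 → 0.95 |
| 0.8 | 0.25 → 0.17 | 0.64 → 0.89 |

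The direction is the same throughout; the size depends on s.

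**5. Does removing the caps make the levels nest?** Not by itself. Bilirubin 1.8×ULN at baseline and 2.5×ULN later meets >2 with baseline ≤2, but fails >1.5 with baseline ≤1.5. CPK can do the same. For ALT and AST this should be rare, because Protocol 4.2.3 excludes patients with confirmed screening values of 2.5×ULN or more. The baseline condition therefore has to be handled along with the caps.

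**The case against.** The case against is substantial, and much of it stands.

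- **The compulsory level is not named.** The note asks for at least one level without saying which, and the asterisk is on the parameter name as well as on the first level. That the first level is the compulsory one is an inference. However, any single level other than the top would still omit the highest values.
- **The top levels are open.** A reader might infer that the worst elevations are lost from the analysis. They are not if all listed levels are reported, which is the natural reading of a commitment to summarise PCSVs as defined in the appendix. What remains is that the text does not require it and that no row counts everyone above the lowest threshold.
- **The appendix calls itself a reference.** True, but the criteria are to be agreed as part of the SAP, and the SAP body points nowhere else.
- **Other displays exist.** SAP 5.1.8.3 plans by-visit summaries, listings with out-of-range flags, and possible shift tables and alternative cut-points. The combined ALT/AST-with-bilirubin criteria are open-ended. Medically relevant abnormalities also enter AE reporting (Protocol 7.4.5; SAP 4.5). These soften the effect considerably. They do not give a between-arm count of isolated ALT, AST or CPK elevations.
- **Repeat samples may fall in the lower band.** Protocol 6.3.4.11 requires significantly abnormal tests to be repeated, and unscheduled on-treatment values count. Scheduled on-treatment chemistry is at weeks 4, 8, 16, 32 and 52, plus early termination. How often a patient with a high peak would also have a value in the lower band cannot be told from the documents. When that happens, being counted depends on resampling and not on severity.
- **The protocol's hepatotoxicity rule does not conflict.** A reader might infer a contradiction from "Alanine aminotransferase (ALT) or aspartate aminotransferase (AST) $>3x$ ULN" in Protocol 5.3.2.1. That phrase is one limb of a rule that also requires raised bilirubin or INR and no other apparent cause. The table's combined criteria already use open-ended ALT/AST above 3 ULN with bilirubin above 2 ULN.

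**Conclusion.** The point holds as a drafting fault in the PCSV definitions, with a modest effect on conclusions. Two things follow from the text alone. First, a table that reports only the marked minimum level omits patients whose only raised values lie above its cap, and even a full set of rows gives no count above the lowest threshold. Second, the cumulative comment contradicts the disjoint bands for bilirubin and CPK; this contradiction does not extend to ALT and AST.

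A reader might go further and infer that fasinumab could be made to look safe on liver enzymes. The documents do not support that. It would require one band to be shown and every other planned laboratory display to be ignored. The 1.0 v 1.83 ratio and the lognormal shares rest on assumed inputs; they show the direction and mechanism, not an expected size in this trial.

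**What to change.** In SAP 11.2 Table 2:

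1. Define the reported levels as open-ended: ALT and AST >3, >5, >10, >20 ULN; total bilirubin >1.5, >2 ULN; CPK >3, >10 ULN.
2. Make at least the lowest open-ended level mandatory for each test.
3. If the levels are to be called cumulative, apply one baseline condition across all levels of a test. It could be the lowest threshold, or the rule in SAP 5.1.8.3 that the value was normal at screening and baseline. The choice should be stated, because the two rules admit different patients. A single condition at the lowest threshold drops patients who start between thresholds, such as the 1.8 to 2.5×ULN bilirubin case; the shift table would show them.
4. Make the comments on all four tests agree with the criteria.
5. Keep the capped bands for the optional shift tables.

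The creatinine criteria carry no optional-level note and need no change on this account.

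The cost is appendix wording and a short edit to each PCSV derivation. No new data are needed. The change should be made before database lock.

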11.3. OMERACT-OARSI set of responder criteria

Note that the criteria in the diagram above are based on standardized score between 0 and 100. For this study, WOMAC pain and physical function score are between 0 and 10, so the absolute change required for response is the required change in the diagram above divided by 10; PGA is 1, 2, 3, 4 or 5, so the absolute change required for response is at least 1 point.

Signature Page for VV-RIM-00075335 v1.0

ESig Approval	 000
---------------	---

ESig Approval	 -2019 09:48:05 GMT+0000
---------------	---

ESig Approval	 19 17:12:43 GMT+0000
---------------	--

ESig Approval	 000
---------------	---

Signature Page for VV-RIM-00075335 v1.0 Approved
